### **8.3. Adverse Events of Special Interest**

#### **Adverse Events of Special Interest**

Combined elevations of aminotransferases and bilirubin, either serious or nonserious and whether or not causally related, meeting the criteria of a potential Hy's Law case (total bilirubin level  $\geq 2 \times$  ULN with simultaneously ALT or AST  $\geq 3 \times$  ULN) should always be reported to the Sponsor as soon as possible following the procedures outlined in Section 8.5 for SAE reporting, with the investigator's assessment of seriousness, causality, and a detailed narrative.

### **8.4. Adverse Event**

#### **8.4.1. Definition of Adverse Event**

An AE is any untoward medical occurrence in a subject administered a pharmaceutical product and that does not necessarily have to have a causal relationship with this treatment. An AE can therefore be any unfavorable and unintended sign (including an abnormal clinical laboratory finding, for example), symptom, or disease temporally associated with the use of a medicinal product, whether or not considered related to the medicinal product (ICH E2A Guideline. Clinical Safety Data Management: Definitions and Standards for Expedited Reporting, October 1994).

It is the responsibility of investigators, based on their knowledge and experience, to determine those circumstances or abnormal clinical laboratory findings which should be considered AEs.

#### **8.4.2. Serious Adverse Event**

An SAE is any untoward medical occurrence that at any dose:

- Results in death
- Is life-threatening
- Requires inpatient hospitalization or prolongation of existing hospitalization
- Results in persistent or significant disability/incapacity
- Is a congenital anomaly/birth defect or
- Is an important medical event

Note: The term "life-threatening" in the definition of "serious" refers to an event in which the subject was at risk of death at the time of the event; it does not refer to an event which hypothetically might have caused death if it were more severe (ICH E2A Guideline. Clinical Safety Data Management: Definitions and Standards for Expedited Reporting, October 1994).

Medical and scientific judgment should be exercised in deciding whether expedited reporting is appropriate in other situations, such as important medical events that may not be immediately life-threatening or result in death or hospitalization but may jeopardize the subject or may require intervention to prevent one of the other outcomes listed in the definition above. Examples

include allergic bronchospasm, convulsions, and blood dyscrasias or development of drug dependency or drug abuse.

Note:

Procedures are not AEs or SAEs, but the reason for the procedure may be an AE or SAE.

Pre-planned (prior to signing the ICF) procedures or treatments requiring hospitalizations for pre-existing conditions that do not worsen in severity are not SAEs.

#### 8.4.3. Severity Assessment

The following definitions should be used to assess intensity of AEs (based on the National Cancer Institute Common Terminology Criteria for Adverse Events [CTCAE], version 5.0):

- Grade 1: Mild; asymptomatic or mild symptoms; clinical or diagnostic observations only; intervention not indicated
- Grade 2: Moderate; minimal, local, or noninvasive intervention indicated; limiting age-appropriate instrumental activities of daily living (eg, preparing for meals, shopping for groceries or clothes, using the telephone, managing money)
- Grade 3: Severe or medically significant, but not immediately life-threatening; hospitalization or prolongation of hospitalization indicated; disabling; limiting self-care activities of daily living (ie, bathing, dressing and undressing, feeding self, using the toilet, taking medications, and not bedridden)
- Grade 4: Life-threatening consequences; urgent intervention indicated
- Grade 5: Death related to AE

#### 8.4.4. Causality Assessment

The investigator should assess causal relationship between an AE and the study drug on the basis of his/her clinical judgment and the following definitions. The causality assessment must be made based on the available information and can be updated as new information becomes available.

- **Related:**
  - The AE follows a reasonable temporal sequence from study drug administration, and cannot be reasonably explained by the subject's clinical state or other factors (eg, disease under study, concurrent diseases, and concomitant medications).

OR

- The AE follows a reasonable temporal sequence from study drug administration, and it is a known reaction to the drug under study or its chemical group, or it is predicted by known pharmacology.
- **Unrelated:**

- The AE does not follow a reasonable sequence from study drug administration, or can be reasonably explained by the subject's clinical state or other factors (eg, disease under study, concurrent diseases, concomitant medications).

#### **8.4.5. Action Taken for Event**

- None
  - No treatment was required.
- Medication required.
  - Prescription and/or OTC medication was required to treat the AE.
- Other.

#### **8.4.6. Adverse Event Outcome**

- Recovered/Resolved
  - The subject fully recovered from the AE with no residual effect observed.
- Recovering/Resolving
  - The AE improved but has not fully resolved.
- Not recovered / Not resolved
  - The AE itself is still present and observable.
- Recovered / Resolved with Sequelae
  - The residual effects of the AE are still present and observable.
  - Include sequelae/residual effects.
- Fatal
  - Fatal should be used when death is a direct outcome of the AE.
- Unknown

### **8.5. Serious Adverse Events Reporting – Procedure For Investigators**

All AEs, AESIs and SAEs will be reported in the eCRF.

The following types of events should be reported by the investigator on a SAVER (Serious Adverse Event Report) form within 24 h of awareness:

- SAEs and SAVERs (see Section 8.4.2 for definition)
- SAEs and AESIs should be reported by the investigator on a Serious Adverse Event Report (SAVER) form within 24 h of awareness (see Section 8.4.2 for the definition of an SAE).

All events (serious and non-serious) must be reported with the investigator's assessment of the event's seriousness, severity, and causality to the study drug. A detailed narrative summarizing

the course of the event, including its evaluation, treatment, and outcome should be provided. Specific or estimated dates of event onset, treatment, and resolution should be included when available. Medical history, concomitant medications, and clinical laboratory data that are relevant to the event should also be summarized in the narrative. For fatal events, the narrative should state whether an autopsy was or will be performed, and include the results if available. Source documents (including medical reports) will be retained at the site and should not be submitted to the Sponsor for SAE reporting purposes.

Urgent safety queries must be followed up and addressed promptly. Follow-up information and response to non-urgent safety queries should be combined for reporting to provide the most complete data possible within each follow-up.

All completed SAVER forms must be signed by the investigator and e-mailed to DSI at the following e-mail address: PPD. See [Section 14.10.5](#) for contact information for SAE reporting. Please call the Sponsor's medical monitor for any questions on SAE reporting ([Section 14.10.4](#)).

Place the initial version of SAVER in the subject's file.

## **8.6. Notifying Regulatory Authorities, Investigators, and Institutional Review Board**

DSI and/or Worldwide Clinical Trials Early Phase Services, LLC will inform investigators, Institutional Review Board (IRB) and regulatory authorities of all SAEs reported from this study, and any Suspected Unexpected Serious Adverse Reaction (SUSAR) occurring in other studies of the investigational drug, as appropriate per local reporting requirements. DSI and/or Worldwide Clinical Trials Early Phase Services, LLC will comply with any additional local safety reporting requirements.

In the US, upon receipt of the Sponsor's notification of SUSARs that occurred with the study drug, unless delegated to the Sponsor, it is the investigator's responsibility to inform the IRB per Sponsor's instruction.

## **8.7. Exposure in Utero During Clinical Studies**

DSI must be notified of any subject who becomes pregnant while receiving or within 90 d of discontinuing the study drug.

DSI must be notified of any male subject whose female partner becomes pregnant while the subject is receiving or within 90 d of discontinuing the study drug. Reporting after ET is done voluntarily by the investigator.

Although pregnancy is not technically an AE, all pregnancies must be followed to conclusion to determine their outcome. This information is important both for drug safety and public health concerns. It is the responsibility of the investigator, or designee, to report any pregnancy in a female subject, or a male subject's female partner, using the exposure in utero (EIU) reporting form. Please contact your study monitor to receive the EIU reporting form upon learning of a pregnancy. The investigator should make every effort to follow the subject until completion of the pregnancy and complete the EIU Reporting form with complete pregnancy outcome information, including normal delivery and induced abortion. The adverse pregnancy outcome,

either serious or non-serious, should be reported in accordance with study procedures. If the outcome of the pregnancy meets the criteria for immediate classification as an SAE (ie, post-partum complications, spontaneous or induced abortion, stillbirth, neonatal death, or congenital anomaly, including that in an aborted fetus), the investigator should follow the procedures for reporting SAEs outlined in Section 8.5.

For reports of pregnancy in the female partner of a male subject, the EIU form (or SAE form if associated with an adverse outcome) should be completed with the subject's randomization number, initials, and date of birth, and details regarding the female partner should be entered in the narrative section.

## 8.8. Clinical Laboratory Evaluations

Blood samples for the following serum chemistry, hematology, and coagulation panels will be performed after at least a 10-h overnight fast at the time points indicated in Appendix 16.5. For clinical laboratory parameters, the reference range at the institution that performs the measurements will be used.

The serum chemistry profiles must be obtained under fasting conditions (approximately 10 h). Results of all laboratory tests will be included in the subject's eCRF.

The following clinical laboratory parameters will be evaluated:

- Serum chemistry (approximately 8.5 mL): sodium, potassium, magnesium, bicarbonate, chloride, calcium, inorganic phosphorus, AST, ALT, GGT, alkaline phosphatase, direct bilirubin, total bilirubin, glucose, creatinine, blood urea nitrogen, total protein, albumin, uric acid, creatine kinase, total cholesterol, and triglycerides.
- Hematology (approximately 4 mL): hemoglobin, hematocrit, red blood cell (RBC) count (with indices), reticulocyte count, white blood cell (WBC) count (with differential), and platelet count.
- Urinalysis: standard urinalysis, including a microscopic examination and specific gravity, pH, protein, glucose, ketones, blood, RBC, WBC, bilirubin, and urobilinogen.

Calculation of eGFR (using the Cockcroft-Gault equation) will be performed at Screening.

Tests for virology (HIV antibody, HBsAg, and HCV antibody) will be performed at Screening only.

Coagulation tests (PT/INR and aPTT).

Child-Pugh Score will be calculated at screening only for the subjects with moderate hepatic impairment for information purpose only.

## 8.9. Vital Signs

SBP, DBP, and pulse will be measured after the subject has rested in a supine position for 10 min or more.

Resting vital signs (blood pressure, heart rate, oral temperature, and respiratory rate) will be performed at Screening, predose and at 2, 24, and 144 h post dose, or Early Termination.

When vital signs measurements and a blood draw are scheduled for the same time point, the vital signs should be taken within approximately 5 min prior to the blood draw. Predose vital signs measurements will be taken at 1 h prior to the dose.

Body weight and height will be recorded at Screening. Body weight will also be recorded at Check-in and at Check-out, or Early Termination. BMI will be calculated at Screening.

Information will be entered in the eCRF on whether or not measured, date of measurement, and measurement results for the following items: SBP, DBP, pulse, respiratory rate, oral temperature, height, body weight, and BMI.

### **8.10. Electrocardiograms**

The ECGs will be read on site as part of the safety assessments. Whether measurement is performed, date performed, results, and findings will be recorded in the eCRF.

The single 12-lead ECGs should be performed after at least 10 min of quiet rest in the supine position (see time points indicated in Appendix 16.5). Before electrodes are removed, the electrode position is to be marked on the skin with indelible ink and the same electrode position used for all subsequent ECGs during confinement for each subject. When a blood draw is scheduled concomitantly with an ECG, the ECG should be taken within 10 min prior to the blood draw. Predose ECGs will be taken at 1 h prior to the dose.

### **8.11. Physical Examinations**

A complete physical examination will be performed by a medically qualified person at the time points indicated in Appendix 16.5. A medically qualified person will perform the physical exam. The physical examination will include an evaluation of the respiratory, cardiovascular, gastrointestinal, dermatological, musculoskeletal, psychiatric, and neurologic systems, as well as the head, eyes, ears, nose, and throat.

### **8.12. Drug and Alcohol Screen**

A urine screen for alcohol, cotinine, and drugs of abuse will be performed for all subjects at Screening and at Check-in. Alcohol, cotinine, amphetamines, barbiturates, benzodiazepines, cocaine, opiates, phencyclidine and cannabinoids will be included in the assay.

### **8.13. Pregnancy Test**

For all female subjects, serum pregnancy tests will be performed at Screening, Check-in and Check-out or Early Termination. Dosing on Day 1 will be contingent upon a negative result.

### **8.14. Serum FSH**

At Screening, should a female subject report postmenopausal status not induced by surgical sterilization, a serum FSH measurement will be obtained.

### **8.15. Other Examinations**

A urine screen for cotinine and drugs of abuse (amphetamines, barbiturates, benzodiazepines, cocaine, opiates, phencyclidine, and cannabinoids) will be performed for all subjects at the time

PL3397-A-U129 Protocol  
Version 2.0, 10 DEC 2019

points indicated in Appendix 16.5. Breath alcohol testing will also be performed at the time points indicated in Appendix 16.5. For female subjects of childbearing potential, a qualitative serum or urine pregnancy test will be performed at the time points indicated in Appendix 16.5. For all postmenopausal female subjects, an FSH test will be performed at Screening.

**9. OTHER ASSESSMENTS**

Not applicable

## **10. STATISTICAL METHODS**

### **10.1. General Statistical Considerations**

All PK and safety data obtained in this study will be displayed in data listings and, if appropriate, summarized using descriptive statistics. A detailed Statistical Analysis Plan (SAP) describing the methodology to be used in the final analysis will be prepared and finalized prior to the database lock. Changes to the statistical analyses will require a protocol amendment only if principal features of the protocol are changed. Any deviations from the planned statistical analyses in the protocol will be fully described in the SAP and the clinical study report.

Categorical data will be presented in contingency tables with cell frequencies and percentages for the subject population.

In general, data will be summarized for the moderate hepatic impairment group and the subjects with normal hepatic function. For point estimations of key PK parameters, 90% confidence intervals (CIs) for HI/normal hepatic function will be calculated (see Section 10.4.1).

For the data analysis, missing data will not be imputed; analyses will be performed on observed data only, unless otherwise noted.

Raw data will be presented with the exact precision with which they were collected.

### **10.2. Analysis Sets**

#### **10.2.1. Pharmacokinetic Analysis Set**

The PK Analysis Set will include all subjects who received a dose of pexidartinib and have sufficient plasma concentration data to characterize the PK parameters. The impact of clinically relevant events that may affect the estimate of PK parameters will be assessed while analyzing data and handled appropriately. Any exclusion will be clearly delineated in the report.

Individual plasma concentrations of pexidartinib and ZAAD-1006a will be reported for all subjects.

#### **10.2.2. Safety Analysis Set**

The Safety Analysis Set will include all subjects who received a dose of pexidartinib.

### **10.3. Study Population Data**

The safety subject population will be summarized for demographic characteristics. Continuous demographic variables (age [calculated from the date of birth to the date when the ICF was signed], body weight, height, and BMI) for all subjects will be summarized with descriptive statistics for both groups. Categorical demographic variables (sex, race, and ethnicity) will be summarized with frequency counts and corresponding percentages.

Medical history data, physical examination data, and prior/concomitant medications will be listed.

## 10.4. Statistical Analysis

### 10.4.1. Pharmacokinetic Analyses

The PK Analysis Set will be used for all PK analyses. Descriptive statistics will be presented for pexidartinib and ZAAD-1006a plasma concentrations at each evaluation time point and for all quantitative PK parameters of pexidartinib and ZAAD-1006a.

Plasma concentration-time data will be analyzed using noncompartmental methods. The following PK parameters of pexidartinib will be calculated using both total and unbound plasma concentrations: Cmax, Tmax, AUClast, AUCinf, kel, t1/2, CL/F, and Vz/F. Plasma PK parameters (Cmax, Tmax, AUClast, AUCinf, t1/2) will be calculated based on both total and unbound plasma concentrations of ZAAD-1006a.

PK parameters for pexidartinib and ZAAD-1006a will be assessed by descriptive statistics for the HI group and matching control group. The metabolite-to-parent ratio for AUClast and AUCinf for total concentrations, adjusted for molecular weight, will be determined for the HI and normal hepatic function groups.

Cmax, AUClast, and AUCinf of pexidartinib (based on total and unbound plasma concentrations) will be compared for the HI group and those of normal hepatic function. These comparisons between the HI group with the matched control group will be made using an analysis of variance model. The resulting point estimates (geometric least squares means), their ratios (HI/normal hepatic function), and 90% confidence intervals (CIs) for the ratios will be presented.

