**Pharmacokinetic Endpoints**

- Pexidartinib: Cmax, Tmax, AUClast, AUCinf, kel, t1/2, CL/F, Vz/F and degree of plasma protein binding.
  - The following PK parameters of ZAAD-1006a will be calculated: Cmax, Tmax, AUClast, AUCinf, t1/2, degree of plasma protein binding
-

PL3397-A-U129 Protocol  
Version 2.0, 10 DEC 2019

---

and metabolite to parent ratio (MPR) for  
AUClast and AUCinf.

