**Statistical Analyses:** **Pharmacokinetics:**  
Descriptive statistics by population (moderate HI and healthy subjects with normal hepatic function) will be presented for pexidartinib and ZAAD-1006a plasma concentrations at each time point and for all PK parameters of pexidartinib and ZAAD-1006a for both total and unbound plasma concentrations.  
Cmax, AUClast, and AUCinf of pexidartinib (based on total and unbound concentrations) will be compared between subjects in the HI group and subjects in the matched control group with normal hepatic function. These comparisons will be made using an analysis of variance model. The resulting point estimates (geometric least squares means), their ratios (HI/normal hepatic function), and 90% confidence intervals (CIs) for the ratios will be presented.  

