#### **2.1.2. Secondary Objectives**

The secondary objectives of this study are:

- To assess the safety and tolerability of pexidartinib after a single oral dose of 200 mg in subjects with normal and moderately impaired hepatic function
- To determine the PK of ZAAD-1006a in subjects with moderate HI, compared to that in healthy subjects with normal hepatic function
- To assess protein binding of pexidartinib and ZAAD-1006a in moderate HI, compared to that in healthy subjects with normal hepatic function

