### **2.2. Study Hypothesis**

This is not a hypothesis testing study. This study will estimate the effect of moderate hepatic dysfunction on the PK of pexidartinib and ZAAD-1006a, compared to a group of healthy subjects with normal hepatic function.

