### **2.3. Study Endpoints**

#### **2.3.1. Primary Endpoints**

##### **Pharmacokinetic Endpoints**

- Pexidartinib: Plasma Cmax, Tmax, AUClast, AUCinf, Kel, t1/2, CL/F, Vz/F, and protein binding
- ZAAD-1006a: Plasma Cmax, Tmax, AUClast, AUCinf, t1/2, MPR based on AUClast and AUCinf, and protein binding

The following unbound PK parameters will be calculated for both pexidartinib and ZAAD 1006a:

- Cmax
- Tmax
- AUClast
- AUCinf

PL3397-A-U129 Protocol  
Version 2.0, 10 DEC 2019

- t1/2

And also for pexidartinib:

- CL/F
- Vz/F

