### **2.3.2. Secondary Endpoints**

#### **Safety Endpoints**

- AEs
- Vital signs
- 12-lead ECGs
- Clinical laboratory tests

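### The protocol sets out to estimate the effect of hepatic impairment on ZAAD-1006a, but plans the HI/normal ratio and 90% CI for pexidartinib only

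*Combined protocol and SAP*

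**What the plan says.** **Aim.** Section 2.2 states: "This study will estimate the effect of moderate hepatic dysfunction on the PK of pexidartinib and ZAAD-1006a", relative to healthy subjects. Section 2.1.2 gives as a secondary objective: "To determine the PK of ZAAD-1006a in subjects with moderate HI, compared to that in healthy subjects with normal hepatic function".

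**Endpoints.** Section 2.3.1 (Primary Endpoints) lists the ZAAD-1006a parameters, including "MPR based on AUC last and AUC inf , and protein binding", and adds "The following unbound PK parameters will be calculated for both pexidartinib and ZAAD 1006a". Section 2.3.2 (Secondary Endpoints) contains safety measures only. The synopsis gives a single PK list without a primary or secondary label.

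**Analysis.** Section 10.4.1 says "PK parameters for pexidartinib and ZAAD-1006a will be assessed by descriptive statistics for the HI group and matching control group". It does not name the statistics. MPR for AUClast and AUCinf, on total concentrations, is to be determined in each group. The between-group model is limited to the parent in both Section 10.4.1 and the synopsis, where the text reads "Cmax, AUClast, and AUCinf of pexidartinib (based on total and unbound concentrations) will be compared between subjects in the HI group". The outputs of that model are geometric least squares means, HI/normal ratios and 90% CIs. Section 10.1 promises 90% CIs for key PK parameters without naming an analyte, and refers the reader to Section 10.4.1.

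**The concern.** The study tests no hypothesis, so its result is an estimate with its precision. The protocol gives the parent exactly that. For the metabolite, which Section 2.2 names alongside the parent, it gives two columns of summaries. Those columns describe each group, but they do not state the contrast between groups or how uncertain it is.

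The protocol's own background makes the metabolite worth estimating. Section 1.2.2 reports that in the earlier HI study the parent was unaffected, while ZAAD-1006a AUC rose by up to about 50% and MPR by up to about 40%. Those figures use Child-Pugh categories, and only 1 subject was moderate on NCI-ODWG criteria. They motivate an estimate here and do not predict its value.

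At stake is a prespecified effect size with its interval. The underlying data are not lost: group summaries are planned, and Section 10.2.1 has individual ZAAD-1006a concentrations reported for all subjects.

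**Working it through.** **1. Promised against planned.**

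| Quantity | Named in the 2.2 estimation aim | Objective (2.1) | Listed under 2.3.1 | HI/normal ratio and 90% CI in 10.4.1 |
|---|---|---|---|---|
| Pexidartinib Cmax, AUClast, AUCinf | Yes | Primary | Yes | Yes, total and unbound |
| ZAAD-1006a Cmax, AUClast, AUCinf | Yes | Secondary, worded as a comparison | Yes | No |
| MPR (AUClast, AUCinf) | Not by name | Not by name | Yes | No |

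Count of planned ratios: pexidartinib 3 × 2 = 6; ZAAD-1006a 0; MPR 0. The general sentence in Section 10.1 adds none, because it points back to Section 10.4.1.

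**2. Is there a figure in the plan to reproduce?** No. Section 10.5 says the sample size of 16 has no statistical basis, and the documents give no CV. The rest of this check illustrates the precision that the missing estimates would have.

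**3. Inputs.** There are 8 subjects per group (Section 10.5) and a 90% two-sided interval (Section 10.4.1). The log scale is implied by geometric least squares means. Between-subject CV is assumed at 20% to 60%; the CV of MPR may differ from that of AUC.

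**4. Formulae.**
- Log-scale SD: σ = √ln(1 + CV²)
- SE of the log ratio: σ√(1/8 + 1/8) = σ/2
- Factor: f = exp(t × SE), with t(0.95, 14 df) = 1.761
- 90% CI: ratio ÷ f to ratio × f

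**5. Results, 8 v 8.**

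| Assumed CV | σ | SE | f | CI at ratio 1.5 | CI at ratio 1.4 | CI at ratio 1.0 |
|---|---|---|---|---|---|---|
| 20% | 0.198 | 0.099 | 1.191 | 1.26–1.79 | 1.18–1.67 | 0.84–1.19 |
| 30% | 0.294 | 0.147 | 1.295 | 1.16–1.94 | 1.08–1.81 | 0.77–1.30 |
| 40% | 0.385 | 0.193 | 1.404 | 1.07–2.11 | 1.00–1.97 | 0.71–1.40 |
| 50% | 0.472 | 0.236 | 1.516 | 0.99–2.27 | 0.92–2.12 | 0.66–1.52 |
| 60% | 0.555 | 0.277 | 1.630 | 0.92–2.44 | 0.86–2.28 | 0.61–1.63 |

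Ratios of 1.5 and 1.4 match the upper end of the AUC and MPR rises reported in Section 1.2.2 and serve only as illustrations. Worked row at CV 40%: σ = √ln(1.16) = 0.385; SE = 0.193; f = exp(1.761 × 0.193) = 1.404; 1.5 ÷ 1.404 = 1.07 and 1.5 × 1.404 = 2.11.

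**6. One dosed subject lost and not replaced (Section 10.5), 7 v 8.** SE = σ√(1/7 + 1/8) and t(0.95, 13 df) = 1.771. The factor becomes 1.199, 1.309, 1.424, 1.542 and 1.662 for the same CVs.

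**7. Reading.** A 1.5-fold observed ratio has an interval that excludes 1 at an assumed CV of 40% or less and includes it at 50% or more. An observed ratio of 1.0 at CV 40% remains compatible with a 40% rise. Side-by-side summaries state neither fact. These are interval widths for an estimation study, not power figures.

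**The case against.** The best defence is that the analysis follows the objectives: the primary objective concerns pexidartinib alone, so the parent gets a model and the metabolite gets description. A place in the Primary Endpoints list does not imply a ratio, since pexidartinib Tmax, kel, t1/2, CL/F and Vz/F are listed there and are only described. Wording an objective as a comparison does not settle it either: the protein-binding objective is worded the same way and has no planned contrast. These points stand, so the listing in 2.3.1 cannot carry the concern alone. They do not answer Section 2.2, which names ZAAD-1006a with the parent in the statement of what is to be estimated.

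Further points:
- Section 10.1 promises listings of all PK data, so anyone could compute the ratio later. That is true, and it limits the loss to prespecification and reporting.
- A separate SAP is due before database lock and could add the comparison. It could. The text supplied contains only the protocol's statistical section, and the finding is confined to that text.
- The factors of 1.19 to 1.63 rest on assumed CVs and apply to any 8 v 8 log-scale comparison. That is correct. They show what the added estimates would deliver and do not measure harm.
- With the same subjects in each analysis, the MPR ratio on the log scale equals the metabolite ratio divided by the parent ratio, so only its interval is new. That is also correct, but the interval cannot be derived from the other two intervals, because it depends on how parent and metabolite vary together within subjects.

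**Conclusion.** The concern holds. The protocol says it will estimate the effect of moderate HI on ZAAD-1006a but prespecifies no metabolite ratio or interval: 6 contrasts for the parent, 0 for ZAAD-1006a and 0 for MPR. This is a gap in estimation and reporting. It raises no error-rate question, because nothing is tested, and it leaves the primary pexidartinib comparison untouched. The textual finding needs no assumption beyond the supplied protocol text. The size of the added intervals depends on the assumed CV of 20% to 60% and on a two-group log-scale model. It is worth correcting because the cost is small and Section 1.2.2 reports that the metabolite rose in the earlier HI study when the parent did not.

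**What to change.** In Section 10.4.1 and the synopsis, and in the SAP when it is written, extend the model planned for pexidartinib, on the log scale, to:
- ZAAD-1006a Cmax, AUClast and AUCinf on total concentrations, and on unbound concentrations if these are to be handled as for the parent;
- MPR for AUClast and AUCinf, on total concentrations only, as Section 10.4.1 defines it.

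Report the HI/normal geometric mean ratio and 90% CI for each, as estimates without multiplicity adjustment. State beside them that the ZAAD-1006a assay is qualified rather than validated (Section 7.1).

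In the same edit, reconcile the status of ZAAD-1006a and MPR across Sections 2.1.2, 2.3.1 and 2.3.2, keeping pexidartinib as the primary comparison. If only description is intended for the metabolite, reword Section 2.2 accordingly, name the descriptive statistics, and still reconcile the endpoint tiers.

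Cost: wording changes plus 3 + 2 = 5 added comparisons on total concentrations, or 6 + 2 = 8 with unbound ZAAD-1006a, beside the 6 already planned. No new samples, subjects or data are needed. The downside is more estimates to report, with wide intervals at 8 v 8.
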